Examining nicotine reinforcement among non-smokers is particularly important given that nonsmokers would be able to modify their behavior, including their dietary caffeine consumption, to prevent vulnerability to the effects of nicotine and potentially prevent a transition from preliminary exposure to regular smoking. Further, there is growing concern about the appeal of non-combustible tobacco products, such as electronic cigarettes, to people who would not choose to use combustible tobacco products. This may be due in part to the perception that e-cigarettes are safer than smoking (Bhalerao et al., 2019; Sears et al., 2017; Walley et al., 2019). Therefore, studying nicotine reinforcement among non-smokers is timely and may inform vulnerability to both smoking and novel methods of nicotine self-administration. Our laboratory has experience examining the reinforcing effects of oral nicotine among non-smokers under rigorous double-blind conditions (i.e., IRB00165287; Duke et al., 2015). Thus, in the present study, we propose to conduct a within-subjects comparison of subjective and reinforcing effects of nicotine following chronic administration of a moderate daily dose of caffeine relative to a placebo maintenance condition. We hypothesize that healthy individuals will report greater positive subjective and reinforcing effects of oral nicotine during chronic caffeine administration relative to the placebo maintenance condition.

4. Study Procedures

a. Study design, including the sequence and timing of study procedures (distinguish research procedures from those that are part of routine care).

Overview. This double-blind, placebo-controlled study will be conducted over a period of approximately 10-12 weeks. Participation may be longer depending on scheduling considerations. The study will assess participants' subjective ratings of the effects of nicotine (one session each for placebo, 1, 2, 3 and 4 mg/70 kg nicotine) and caffeine (one session of 300 mg caffeine) across two conditions compared within-subjects: a caffeine maintenance condition (4-5 weeks) and a placebo maintenance condition (4-5 weeks). The order in which caffeine and placebo maintenance conditions are administered will be counterbalanced across participants. Figure 1 shows a study overview.

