Dietary restrictions. In order to reduce possible caffeine withdrawal effects on the assessment of the reinforcing effects of caffeine, enrolled subjects will be required to remain caffeine abstinent throughout the study. As in some of our previous studies (e.g., IRB00165287; Sigmon & [name],

Figure 1. Illustrative sequence of study conditions with the Caffeine Maintenance condition first. Caffeine and Placebo Maintenance conditions will be counterbalance across participants.

Fig 1. Illustrative participation timeline including screening, caffeine maintenance, and placebo maintenance. All doses of drug and placebo are administered orally in capsules. The order of caffeine maintenance and placebo maintenance will be counterbalanced across participants and the multiple-choice session and end-of-study survey visit will always occur after the second maintenance condition. Total participation will consist of 19 visits including 1 screening visit, 4 food diary visits, 12 experimental sessions, 1 multiple-choice reinforcement session, and 1 final visit to complete the end-of-study survey. We estimate participation will occur across 10-12 weeks. Participation may be longer depending on scheduling considerations.

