Experimental sessions during caffeine maintenance. After receiving caffeine maintenance for at least one week, participants will continue daily caffeine administration and will also be exposed to experimental test sessions across approximately 3-4 weeks (one session each for placebo, 1, 2, 3 and 4 mg/70 kg nicotine and 300 mg caffeine). The purpose of the nicotine sessions is to assess the subjective and reinforcing effects of nicotine, whereas the purpose of the caffeine session is as a manipulation check to test tolerance to caffeine during caffeine maintenance relative to placebo maintenance. The order in which the different doses for experimental sessions are received will be counterbalanced across participants. Subjects will report to the laboratory approximately 2-3 times per week, depending on schedule considerations. Sessions will be separated by at least 48 hours (e.g., Monday, Wednesday, Friday sessions). At each visit, participants will provide a saliva sample, complete pre-drug subjective questionnaires, and orally ingest study capsules with water under double-blind conditions. After leaving the laboratory, outcome measures will be assessed at 1, 2, 3, and 4 hours post-capsule administration.

Measures will include subjective ratings of drug effects (e.g., energetic, drowsy/sleepy, elated, jittery/shaky) and surrogate measures of reinforcement such as liking, take again, and the multiplechoice reinforcement procedure, which we have used in previous research. These questionnaires will be completed online using Qualtrics survey technology, including via the Qualtrics App while in the laboratory, or using conventional paper forms. When participants are completing their surveys online, a survey link will be sent to them via email or text message. Paper forms of surveys will be provided as a back-up in the event of technical issues with administering surveys via Qualtrics, in the event of difficulties with participant compliance for online assessments, or in the event the participant does not have a smart phone or computer access. The multiple-choice procedure will assess participant preference for "today's drug" over various amounts of money ranging from -\$30 (i.e., forego \$30 rather than receive "today's drug") to \$30 (i.e., receive \$30 rather than receive "today's drug").

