Participants may voluntarily withdraw from the study at any time. They may also be removed if they have a significant adverse effect that we judge likely to be a reaction to a study drug, if they are noncompliant with study procedures or restrictions, if they become pregnant, or if new information becomes available that suggests continued study participation would put them at increased risk of adverse events.

g. Description of what happens to participants receiving therapy when study ends or if a participant's participation in the study ends prematurely.

The proposed study is not a treatment study and participants are healthy volunteers. Neither study participation nor its termination will affect the ability of the participants to seek treatment services. Participants may withdraw from the study at any time without loss of benefits.

5. Inclusion/Exclusion Criteria

Inclusion Criteria

- 1. Participant age is 18-45 years.
- 2. Participant regularly consumes caffeine (e.g., at least once weekly or at least approximately 3 times per month).
- 3. Participant has less than 100 lifetime exposures to tobacco or nicotine-containing products (i.e., accepted definition of a never smoker according to the U.S. Centers for Disease Control).
- 4. Participant has no nicotine use in the last year.
- 5. The subject must be in good health as determined by medical history and vital signs.
- 6. Participant Body Mass Index (BMI) must be between 18.5 and 34.9 (BMI<18.5 = Underweight; BMI>34.9 = moderate-to-high-risk Obese).
- 7. The subject is fluent in English (speaking, writing, and reading) and is capable of understanding and complying with the protocol.
- 8. Females: Females of childbearing potential must agree to use appropriate birth control (barrier methods, hormonal contraceptives, and/or intrauterine devices) during the entire duration of the study. Females who are not of childbearing potential must be postmenopausal for 2 years or have a history of hysterectomy and/or oophorectomy.

Exclusion Criteria

- 1. Subjects with known hypersensitivity or medical contraindication to the study drugs.
- 2. Subjects with a significant current neurological, hepatic, renal, endocrine, cardiovascular, gastrointestinal, pulmonary or metabolic disease for which administration of the study drugs would be contraindicated.

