Both study drugs to be administered are legally marketed in the United States. Further, the study does not involve a route of administration, dose, or patient population that significantly increases the risk (or decreases the acceptability of the risk) associated with the use of the drug. Previous research has demonstrated that caffeine (Sigmon & [name], 2011) and nicotine (Duke et al., 2015) at the proposed doses (or indeed at higher doses) and the proposed route of administration (oral) are well-tolerated in non-drug-abusing volunteers. The maximum study dose of nicotine is consistent with what is currently available over-the-counter in oral form (e.g., 4 mg lozenges or gum). Caffeine is readily available over-the-counter in medications, supplements, beverages, and foods. The study is not intended to be reported to FDA in support of a new indication or to support any other change in labeling of the drugs. The study does not intended to promote or commercialize the drug products. As such, the proposed investigation is exempt from IND requirements because all of the criteria for an exemption in FDA regulations § 312.2(b) are met.

c. Justification and safety information if non-FDA approved drugs without an IND will be administered.

N/A

7. Study Statistics

a. Primary outcome variable.

Primary outcome measures will be participant ratings assessed pre-drug and at 1, 2, 3, and 4 hours post capsule administration during the experimental test sessions examining placebo, nicotine, and caffeine. Primary outcomes include subjective ratings (e.g. Subjective Effects Questionnaire, and surrogate measures of reinforcement such as liking, take again, monetary value). Primary outcomes will be compared within-subjects across the caffeine maintenance condition and the placebo maintenance condition.

b. Secondary outcome variables.

Secondary outcome measures will be subject demographic characteristics, drug use history, personality factors (e.g., sensation seeking), and decision-making factors (i.e., delay discounting) that will be examined as they correlate to positive subjective effects of nicotine during the experimental test sessions.

c. Statistical plan including sample size justification and interim data analysis.

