Subjective and reinforcing effects of nicotine (e.g., drug liking, take again, monetary value) will be examined as a function of nicotine dose and caffeine maintenance. Repeated measures ANOVAs will be conducted with caffeine maintenance phase (caffeine vs. placebo), drug dose (placebo and 4 doses of nicotine) and time (1, 2, 3, and 4 hours, as appropriate) as within-subjects factors. It is anticipated that there will be a significant drug dose by maintenance phase interaction such that positive subjective ratings on active nicotine sessions will be greater (and more differentiated from placebo) during the caffeine maintenance phase relative to the placebo maintenance phase. A sample size of 11 was previously sufficient to detect significant differences in nicotine reinforcement within subjects as a function of caffeine maintenance in an inpatient study (Jones & [name], 2003). In order to facilitate the exploration of effects of demographics (e.g., age, sex) and previous caffeine use, and to account for additional variability in an outpatient study, we propose a larger sample size of 36. This sample size is consistent with previous outpatient studies conducted by our laboratory that manipulated caffeine maintenance and examined differences in caffeine subjective effects (Evans & [name], 1992). The appropriateness of the proposed sample size is supported by a formal power analysis for repeated measures ANOVA examining an interaction between drug dose (five observations: placebo and four doses of nicotine) and caffeine maintenance (two levels treated as groups in the power analysis, thus conservatively assuming no correlation for this within-subjects factor) assuming an effect size of .20, correlation among repeated measurements of .5, desired power of .8, and $\alpha = .05$.

It is anticipated that in order to have 36 participants successfully complete the study, approximately 60 participants may have to be enrolled in order to allow for the possibility of participant dropout (i.e., attrition of up to 40% of enrolled participants). In order to obtain 60 enrolled participants, we anticipate that as many as 150 individuals may need to be consented and screened for study eligibility during the in-person Screening session (i.e., a screening failure rate of approximately 60%).

d. Early stopping rules.

There are no early stopping rules in this study.

8. Risks

a. Medical risks, listing all procedures, their major and minor risks and expected frequency.

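### The repeated measures ANOVA leaves out the order group of a counterbalanced two-period crossover, so any period effect stays in the error term

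*Combined protocol and SAP*

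**What the plan says.** Section 4a (Overview) sets up a two-period crossover: "The order in which caffeine and placebo maintenance conditions are administered will be counterbalanced across participants". The Figure 1 legend repeats this. Within each condition, section 4a also states: "The order in which the different doses for experimental sessions are received will be counterbalanced across participants".

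Section 7a says: "Primary outcomes will be compared within-subjects across the caffeine maintenance condition and the placebo maintenance condition". Section 7c gives the model as repeated measures ANOVAs with maintenance phase (caffeine or placebo), dose (placebo and four nicotine doses) "and time (1, 2, 3, and 4 hours, as appropriate) as within-subjects factors". The predicted result is stated there: "It is anticipated that there will be a significant drug dose by maintenance phase interaction".

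No section adds an order, sequence or period term. The covariates named in section 4a are demographic, personality and delay-discounting measures, intended to explain individual differences in drug response. Section 7c plans for 36 completers out of 60 enrolled, with "attrition of up to 40% of enrolled participants".

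**The concern.** In a two-period crossover, a period effect moves the caffeine-minus-placebo difference up in one order group and down in the other. With equal groups the shifts cancel in the mean, but they remain as extra spread between people. If order is not in the model, that spread goes into the error term.

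Two tests have to be separated. The overall phase comparison takes the full effect of a period shift. The dose x phase test, which carries the prediction and the sample size, compares doses within a phase, so a shift common to all doses drops out. Only a period effect that differs by dose reaches it. Counterbalancing dose order spreads general session trends over the doses, which leaves a change in nicotine response between the first and second phase. That is plausible here, because section 5 requires that "Participant has less than 100 lifetime exposures to tobacco or nicotine-containing products" and no nicotine use in the last year, and everyone scheduled for the second phase has been through the nicotine sessions of the first. The documents neither describe such a change nor give a size for it.

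Counterbalancing is promised at assignment. Nothing secures balance among completers when up to 40% may drop out.

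**Working it through.** **Plan's own figure.** Inputs from section 7c: f = .20, correlation rho = .5, m = 5 measurements, 2 groups, alpha = .05, N = 36. Noncentrality = f² x N x m / (1 − rho) = 0.04 x 36 x 5 / 0.5 = 14.4.

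- Univariate F (df 4 and 136): power .864 at 36; 32 would be enough for .80.
- Multivariate F (df 4 and 31): power .816 at 36; 35 gives .801, which rounds up to 36 for two equal groups.
- Counting 36 people as 72 observations gives .995.
- Enrolment: 36 / (1 − .40) = 60.

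So 36 is reproduced. The calculation has no period or order term.

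**Set-up for the check.** Let pi be the period 1 minus period 2 difference, in SDs of the per-person contrast being tested. It is an assumption, shown at 0.3, 0.5 and 0.75. The caffeine-minus-placebo difference is then tau + pi in the caffeine-first group and tau − pi in the placebo-first group, plus error with SD 1. For 80% power with 36 people and no period effect, tau = 0.48. Dose x phase was simulated as a 2 x 5 within-subject ANOVA on time-averaged scores under sphericity, with both the interaction and any period x dose effect shaped as all active doses against placebo.

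**Phase comparison, 18:18, order omitted.** The standard error is multiplied by sqrt(1 + pi² x 36/35), which is 1.045, 1.121 and 1.256.

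| pi (SD) | 0 | 0.3 | 0.5 | 0.75 |
|---|---|---|---|---|
| Phase: power | .80 | .77 | .73 | .63 |
| Phase: type I error | .05 | .040 | .028 | .015 |
| Dose x phase, period effect varying by dose: power | .80 | .79 | .77 | .73 |
| Same, from the plan's inputs: power | .86 | .85 | .84 | .81 |
| Dose x phase, period effect varying by dose: type I error | .05 | .044 | .038 | .030 |

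With order in the model, both tests return to about .05 and to their baseline power. On the 72-observation reading, the dose x phase loss is under .01.

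**Dose x phase, common period effect.** With a shift of 0.75 SD of the difference at one dose, type I error is .047 to .050 and power .80, at both 18:18 and 24:12. Nothing is lost.

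**Session trend common to all doses.** The trend is linear over the 12 sessions, 0.5 or 1.0 SD from first to last, with dose order random within each phase, at 18:18. Dose x phase power is .79 and .77 with or without order, so order recovers nothing there. Type I error for phase is .022 and .003 without order, and .049 and .053 with it.

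**Unequal completers.** The phase estimate shifts by pi x (n1 − n2)/36. At pi = 0.5 this is 0.5 x 6/36 = 0.083 SD at 21:15 and 0.5 x 12/36 = 0.167 SD at 24:12.

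| Split, pi = 0.5 | Type I error without order: phase / dose x phase | Power without order, by which order has more completers: phase; dose x phase | Power with order |
|---|---|---|---|
| 21:15 | .050 / .050 | .86 or .55; .89 or .61 | .79 |
| 24:12 | .118 / .086 | .94 or .37; .95 or .45 | .74 to .75 |

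**How likely such splits are.** If 30 per order enrol and dropout is unrelated to order, a gap of 6 or more has probability .147 (two independent binomials with 60% completion) to .187 (exactly 36 of 60 complete). A gap of 12 or more has probability .002 to .003. Averaged over chance splits, for the three values of pi, type I error is .046, .037 and .028 (phase) and .048, .044 and .037 (dose x phase).

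**The case against.** The strongest reply is that the test the plan relies on is barely touched. Both the prediction and the power analysis concern dose x phase. A common period effect costs it nothing, and from the plan's inputs even a dose-varying one leaves power at .85, .84 or .81, still at or above the desired .80. The larger loss falls on the phase main effect, which averages placebo with nicotine sessions and on which no sample size rests.

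The assumed range also starts at 0.3 SD without support in the documents; at 0.1 and 0.2 SD, power for either test stays at about .80 and .79. The inflated type I errors need a 24:12 split, which chance almost never gives.

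All of that is correct, and it limits the weight of the point. Three things remain:

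- On the multivariate reading of the power calculation, the baseline is .816, so there is less margin.
- Section 7a states the comparison between conditions for the primary outcomes, and section 7c predicts ratings on active nicotine that are higher under caffeine as well as better separated from placebo. The first part of that prediction is a phase difference at active doses, from which a period effect does not cancel. The caffeine-tolerance check in section 4a is also a comparison between phases.
- A 21:15 split is not rare. There, power without order can be well above or below the adjusted figure, depending only on which order lost more people.

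**Conclusion.** The concern holds as a modest one. The design controls order and the analysis ignores it. With completers balanced by order, the planned tests are not invalidated; they become conservative. At 0.3, 0.5 and 0.75 SD, phase power falls from .80 to .77, .73 and .63. Dose x phase is unaffected by a common period effect and falls to .79, .77 and .73 if the effect differs by dose.

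With unequal completers, the estimate shifts and the tests need not be conservative. Chance imbalance gives no bias on average. Systematic bias would need dropout related to order, for which there is no figure.

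These sizes rest on an assumed period effect, 1:1 assignment to order (the ratio is not stated), sphericity, and one shape of interaction. A period effect linear across doses shows the same pattern. With each order group's difference moved in opposite directions by 0.5, 1 or 2 error SDs of a single-dose difference from lowest to highest dose, dose x phase power is .78, .72 and .47 without order and about .80 with it.

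The change should be made because it is nearly free, and not because harm has been demonstrated.

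**What to change.** In section 7c, add order group (caffeine-first or placebo-first) as a between-subjects factor, with its interactions with phase, dose and phase x dose. Order x phase is then the period effect, and order x phase x dose is the period effect that differs by dose. Estimate the phase and phase x dose effects with equal weight on the two orders, and report the number of completers in each. Specify this before unblinding, so that including order is not a choice made after seeing the data.

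The cost is a sentence in the plan and no new data. Error degrees of freedom go from 35 to 34 for phase and from 140 to 136 for dose x phase. If there is no period effect, power is unchanged at 18:18, about .79 instead of .80 at 21:15, and about .74 to .75 at 24:12, so equal weighting costs most where completers are most unequal. The change does not remove differential carryover between the two maintenance conditions.
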